9.1. Demographic and Other Baseline Characteristics

Summaries of age, weight, height, BMI, sex, ethnicity, and race will be presented by BAL sampling timepoint and for all subjects (Table 8, Table 9). Ethnicity is categorized as Hispanic or Latino, not Hispanic or Latino, Not Reported, and Unknown. In accordance with NIH reporting policy, subjects may self-designate as belonging to more than one race or may refuse to identify a race, the latter reflected in the CRF as "No" to each racial option.

Individual subject listings will be presented for all demographics (Listing 5).

9.1.1. Prior and Concurrent Medical Conditions

All current illnesses and past pre-existing medical conditions will be coded using MedDRA dictionary version 20.1 or higher. Summaries of subjects' pre-existing medical conditions by MedDRA system organ class (SOC) and BAL sampling timepoints will be presented in Table 10. Individual subject listings will be presented for all medical conditions (Listing 6).

9.1.2. Prior and Concomitant Medications

Prior (30 days before administration of the first dose) and Concomitant medications will be coded to the Anatomical Therapeutic Classification (ATC) using the WHO Drug Dictionary. The use of prior or concomitant medications during the study will be summarized by ATC1 and ATC2 code and BAL sampling timepoint for the Safety Population (separately in Table 33 for prior medications and Table 34 for concomitant medications). Individual subject listings will be presented for all prior and concomitant medications). Individual subject listings and Listing 19 for concomitant medications).

Drugs will be listed and summarized as prior medications when the end date for the medication is before the first dose of study product and listed and summarized as concomitant medications otherwise.

9.2. Measurements of Treatment Compliance

The infusion start and end dates and times for each dose of study product will be listed (Listing 7).

9.3. Adverse Events

TEAEs will be collected from the start of the first infusion on Day 1 through the Telephone Follow-Up Interview on Day 3. When calculating the incidence of AEs (i.e., on a per subject basis), each subject will only be counted once at the highest severity recorded and any repetitions of AEs within a subject will be ignored. Denominators for percentages are the number of subjects in the Safety Population.

9.3.1. Unsolicited Adverse Events

A brief overall summary of AEs will be shown in Table 11, including the number of subjects with at least 1 TEAE of any severity, the number of subjects with at least 1 related TEAE of each severity, and the number of subjects with at least 1 SAE.

The following summaries for unsolicited TEAEs will be presented by MedDRA system organ class (SOC) and Preferred Term:

- The total number of TEAEs and the number and percentage of subjects reporting at least one AE, regardless of severity or relationship to study product. 95% CI intervals will be presented for proportions (Table 12), following start of each infusions and for any time from the start of infusion for Dose 1 through the Telephone Follow-Up Interview on Day 3.
- The total number of TEAEs and the number and percentage of subjects reporting at least one AE by severity and relationship to study product (Table 13), for all AEs occurring from the start of infusion for Dose 1 through the Telephone Follow-Up Interview on Day 3.
- Bar chart displaying the incidence (number of subjects) of related TEAEs by severity and MedDRA SOC (Figure 3);
- Bar chart displaying the frequency (number of occurrences) of related TEAEs by severity and MedDRA SOC (Figure 4);

AEs by subject will be presented in Listing 8. A subject listing of non-serious AEs of moderate or greater severity will be reported (Table 15).

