#### DMID/NIAID/NIH

#### CONFIDENTIAL

sampling time. Ten additional enrolled subjects will act as alternates to obtain 30 evaluable subjects.

Each subject will complete Screening, Baseline, Treatment and Follow-up Phases. The Screening Phase will be conducted on an outpatient basis within 30 days of the Baseline Phase, which will consist of admission to DEPRU on the day before the first dose (Day -1) for pre-dosing assessments. The Treatment Phase will start on the day of first dose (Day 1) and end at the time of discharge from DEPRU. Three IV doses of ZTI-01 will be administered every 8 hours (hours 0, 8, and 16 during the Treatment Phase). Blood samples for PK measurements will be collected before each dose, up to 8 hours after the start of the first IV infusion of ZTI-01, and up to 12 hours after the start of the third IV infusion (Tables 2 and 3). One bronchoscopy with BAL will be completed on each subject at the timepoint to which that subject was randomized. Key electrolytes will be remeasured prior to each subject's bronchoscopy in order to minimize risk of arrhythmia. Subjects will be discharged following the final 12-hour blood sampling time point (if safety parameters are acceptable to the Investigator). Safety assessments will be conducted during the entire 24-hour Treatment Phase. The Follow-Up Phase consists of a telephone interview on Day 3 for symptom-driven safety assessments.

Estimated Time to Complete	
Enrollment:	

Approximately 12 weeks

DMID/NIAID/NIH

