#### 9.2.3. Procedures to be Followed in the Event of Abnormal Laboratory Test Values or Abnormal Clinical Findings

A licensed study physician will make the determination of seriousness, severity, and causality, provide a medical evaluation of adverse events, and classify adverse events based upon medical judgment. Abnormal laboratory test values or abnormal clinical findings for all enrolled subjects, including values and findings noted at screening and baseline, will be assessed using the toxicity scales in Appendix B. Abnormal values and findings noted at Screening or Baseline will only be considered AEs if they increase in grade after study product administration. For abnormalities noted from the time of study drug administration, any Grade 1 or higher laboratory abnormality listed on the toxicity table in Appendix B will be entered in the database as an AE. Abnormal clinical/laboratory findings will be collected, assessed, documented, reported, and followed appropriately.

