4.2. Discussion of Study Design, Including the Choice of Control Groups

As the main focus of this protocol is to evaluate the safety and pharmacokinetics of multiple doses of ZTI-01, there is no control group and all subjects receive the same dose of ZTI-01with the same PK blood collection timepoints. Subjects will be randomized to one of five BAL sampling timepoints with a total of 6 subjects assigned to each BAL sampling time.

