4.5.1. Safety Variables

The type, incidence, relatedness, and severity of TEAEs and SAEs will be recorded from time of first dosing on day 1 through the follow-up call on Day 3. Refer to Section 3.3 for definitions of AEs, TEAEs, SAE, severity and relatedness.

The following safety laboratory parameters and vital signs will be summarized for baseline and each postdose timepoint collected. Change from baseline will be summarized for all post dose timepoints. The most recent measurement prior to start of infusion of the first ZTI-01 dose will be regarded as baseline. For parameters with multiple pre-dose measurements, screening values prior to the baseline measurement will be listed only.

Serum chemistry:

- Albumin, glucose, blood urea nitrogen (BUN), potassium, magnesium, calcium, sodium, total protein, creatinine, triglycerides, total cholesterol, creatine phosphokinase (CPK), phosphorus, alkaline phosphatase (ALP), aspartate aminotransferase (AST), alanine aminotransferase (ALT), total bilirubin, direct bilirubin, and lactate dehydrogenase (LDH) will be collected at Screening and Day 2 before discharge. Albumin, random glucose, BUN, potassium, magnesium, calcium, sodium, phosphorus, total protein, creatinine, CPK, ALP, AST, ALT, and total bilirubin will be collected at Baseline (Day - 1 to Day 1). Sodium, potassium, magnesium, calcium, and phosphorus will be collected approximately 2 hours prior to the assigned bronchoscopy timepoint.

Hematology:

- Hemoglobin, hematocrit, platelet count, white blood cell (WBC) count, neutrophils, lymphocytes, monocytes, eosinophils, basophils will be collected at Screening and Day 2 before discharge.

Coagulation:

- Prothrombin time (PT) and activated partial thromboplastin time (aPTT) will be collected at Screening and Day 2 before discharge.

Urinalysis:

- Leukocyte esterase, blood, pH, specific gravity, glucose, protein. A microscopic test will be performed if urinalysis is abnormal. The microscopic urinalysis result for the presence of blood will supersede the dipstick urinalysis result. Urinalyses performed at Screening and Day 2 before discharge.

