4.5.2. Pharmacokinetics Variables

Blood (plasma) for PK samples will be drawn for all subjects at the following timepoints relative to each dose:

- Dose 1: Within 10 minutes before starting the 1-hour infusion and at 30 minutes (±5 minutes), 1 hour (0 to 5 minutes from end of infusion), 1 hour 15 minutes (±5 minutes), 2 hours (±5 minutes), 5 hours (±15 minutes) from the start time of the first infusion of ZTI-01
- Dose 2: Within 10 minutes before starting the second 1-hour infusion.

Note: This PK sample will be reported as the 8 hours post Dose 1 PK sample

Dose 3: Within 10 minutes before starting the 1-hour infusion and at 30 minutes (±5 minutes), 1 hour (0 to 5 minutes from end of infusion), 1 hour 15 minutes (±5 minutes), 2 hours (±5 minutes), 5 hours (±15 minutes), 8 hour (±15 minutes), and 12 hours (±15 minutes) from the start time of the third (last) infusion of ZTI-01

A standardized bronchoscopy with BAL sampling will be performed at ± 15 minutes of the single assigned timepoint based on each subject's schedule assignment: 30 minutes, 1 hour 15 minutes, 2, 5, or 8 hours after the start time of the third (last) infusion of ZTI-01.

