14.3.1.2 Unsolicited Adverse Events

Table 12: Summary of Unsolicited Adverse Events by MedDRA System Organ Class and Preferred Term, and Timepoint

ModDDA System	ModDDA		Start of Pr	of Infusion 1 – Pre-Dose 2 (N=X)		Start of Infusion 2 – Pre-Dose 3 (N=X)				Start of Infusion 3 – Follow-Up (N=X)				Any Time Post Start of Infusion (N=X)			
Organ Class	Preferred Term	n	%	95% CI	Events	n	%	95% CI	Events	n	%	95% CI	Events	n	%	95% CI	Events
Any SOC	Any PT	х	XX	xx, xx	х	х	XX	xx, xx	х	х	XX	xx, xx	х	х	XX	xx, xx	х
[SOC 1]	Any PT																
	[PT 1]																
	[PT 2]																
[SOC 2]	Any PT																
	[PT 1]																
	[PT 2]																
Notes: N = Number of su (n) and corresponding p	bjects in the Safety Po bercent (%), a subject	pulation is only o	n who sta	rted the spe nce per Pre	cified infus ferred Tern	sion. Thi n and tin	s table p nepoint.	presents nur	nber and p	bercenta	age of sub	pjects and th	e number o	f events.	For the 1	number of su	ibjects

Table 13:Unsolicited Adverse Events by MedDRA System Organ Class and Preferred Term,
Maximum Severity and Relationship

ModDRA System			All Subjects (N = X)								
Organ Class	Preferred Term	Severity		Relat	ed		Not Rela	ated			
			n	%	Events	n	%	Events			
Any SOC	Any PT	Any Severity	х	х	Х	х	х	х			
		Mild	х	х	Х	х	х	х			
		Moderate	х	х	Х	х	х	х			
		Severe	х	х	Х	х	х	Х			
SOC 1	PT 1	Any Severity	х	x	Х	х	х	Х			
		Mild	х	x	Х	х	х	Х			
		Moderate	х	x	Х	х	х	Х			
		Severe	х	x	Х	х	х	Х			
	PT 2	Any Severity	х	x	Х	х	х	Х			
		Mild	х	х	Х	х	х	Х			
		Moderate	х	х	Х	х	х	Х			
		Severe	х	х	Х	х	х	х			
Note: N = Number of su	ubjects in the Safety Popu	ilation.				•	•	•			

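### SAP Table 12 gives AE percentages by dose window over everyone infused, although scheduled laboratory and ECG detection is nil in the Dose 1 window and over 90% of graded laboratory results come after Dose 3

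*SAP*

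**What the plan says.** **The table.** SAP 9.3.1 states that "95% CI intervals will be presented for proportions (Table 12), following start of each infusions and for any time" from Dose 1 to the Day 3 call. The shell, titled "Summary of Unsolicited Adverse Events by MedDRA System Organ Class and Preferred Term, and Timepoint", has four column groups: infusion 1 to just before Dose 2, infusion 2 to just before Dose 3, a third labelled "Start of Infusion 3 – Follow-Up (N=X", and any time after the first infusion starts. Its note sets N to members of the Safety Population who began the infusion in question. SAP 6.1 makes intervals for percentages Clopper-Pearson.

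**What counts as an AE.** Under Protocol 9.2.3, once dosing has begun, "any Grade 1 or higher laboratory abnormality listed on the toxicity table in" Appendix B is entered as an AE. ECG intervals are graded in Protocol Table 10 and SAP Table 4.

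**When tests are done.** The Protocol Summary says "Three IV doses of ZTI-01 will be administered every 8 hours (hours 0, 8, and 16 during the Treatment Phase". SAP 4.5.1 says "Sodium, potassium, magnesium, calcium, and phosphorus will be collected approximately 2 hours prior to the assigned bronchoscopy timepoint". SAP 4.5.2 places the bronchoscopy at "30 minutes, 1 hour 15 minutes, 2, 5, or 8 hours after the start time of the third (last) infusion of ZTI-01", and SAP 4.2 randomizes subjects "with a total of 6 subjects assigned to each BAL sampling time". All other post-dose chemistry, and all post-dose hematology, coagulation and urinalysis, is taken on Day 2 before discharge. Discharge is at least 12 h after infusion 3 starts (SAP 4.1). The one scheduled ECG on treatment follows Dose 3. Vital signs are taken at the same four times after the start of every infusion.

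Neither SAP 9.3.1 nor the shell separates test-detected AEs from the rest or comments on test timing.

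**The concern.** A percentage with an interval in a dose window implies that the subjects in the denominator could have shown the event in that window. For laboratory and ECG AEs this is untrue of the Dose 1 window, and only partly true of the Dose 2 window. An empty Dose 1 cell would mean that nobody was tested, yet it would print as an observed zero with an upper confidence limit.

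This bears on the signals the protocol leads one to expect. In Protocol Table 4 the three most frequent AEs on ZTI-01 are laboratory findings: raised ALT (8.6%), raised AST (7.3%) and hypokalemia (6.4%). Protocol 2.3.1 lists QT prolongation as common. The safety objective concerns multiple doses, and Table 12 is the only AE summary table split by dose, so readers will compare its columns.

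**Working it through.** **1. The plan's own detection figure.** Protocol Table 8 is 1 − (1 − p)^30. At p = 2% this gives 45.5% (printed 45%), at 5% 78.5% (79%) and at 10% 95.8% (96%). All eight rows reproduce. The formula assumes that all 30 subjects are observed for the event. That suits the any-time column. With no subject tested, as in the Dose 1 window, the probability of a scheduled detection is 1 − (1 − p)^0 = 0.

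**2. Time of the electrolyte draw.** It is 16 h + BAL time − 2 h.

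| BAL group (6 each) | From infusion 3 start | From infusion 1 start |
|---|---|---|
| 0.5 h | −1.5 h | 14.5 h |
| 1.25 h | −0.75 h | 15.25 h |
| 2 h | 0 h | 16 h |
| 5 h | +3 h | 19 h |
| 8 h | +6 h | 22 h |

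None falls in hours 0 to 8. Two groups (12 subjects) fall in the Dose 2 window, or three (18) if the 2-h group's draw precedes infusion 3.

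**3. Is there another draw?** Protocol Appendix A marks laboratory tests under the Treatment Phase, but its footnote gives no additional time. Appendix C counts one chemistry, one electrolyte, one hematology and one coagulation sample for treatment and discharge together. Its column total confirms this: 9 + 4.5 + 4 + 2.7 + 4 (urea) + 60 (PK) = 84.2 mL, as printed.

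**4. Scheduled coverage, 30 continuing subjects.** Protocol Table 11 grades 19 chemistry, 6 hematology, 2 coagulation and 3 urine parameters, 30 in all.

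| Window | Subjects with a laboratory test | Parameters | ECG |
|---|---|---|---|
| Dose 1 | 0/30 | none | 0/30 |
| Dose 2 | 12/30 to 18/30 | 5 electrolytes | 0/30 |
| Dose 3 | 30/30 | all 30 | 30/30 |

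Graded results total 30 × (30 + 5) = 1,050. Before Dose 3 there are 12 × 5 = 60 (5.7%) to 18 × 5 = 90 (8.6%). After Dose 3 there are 990 (94.3%) to 960 (91.4%).

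**5. What Table 12 would print with no dose effect.** Assume that an abnormality is present from Dose 1 in a share p of subjects, persists, and counts as one AE in the window where it is first detected.

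- Non-electrolyte laboratory or ECG AE: 0%, 0%, p. At p = 10%: 0%, 0%, 10%. Over p = 5% to 30% the last figure is 5% to 30%.
- Electrolyte AE: 0%, then 0.4p to 0.6p, then the remaining 0.6p to 0.4p. Protocol 2.1 reports decreased calcium in 10.7% after 8 g. With that p: 0%; 0.107 × 0.4 = 4.3% to 0.107 × 0.6 = 6.4%; then 6.4% to 4.3%.

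**6. The interval on the untested cell.** The Clopper-Pearson upper limit for 0/30 is 1 − 0.025^(1/30) = 11.6%.

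**7. The any-AE row.** Assume evenly observed clinical AEs at a constant 20% per window, independent of a non-electrolyte laboratory AE in a share p. Window 1 shows 20%. Window 3 shows 1 − 0.8 × (1 − p): 28% at p = 10% and 44% at p = 30%.

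**The case against.** **Other outputs show the timing.** SAP Tables 20 to 27 give laboratory results at their actual timepoints, Tables 31 and 32 do so for ECG, and Listing 8 gives dose number and hours post dose for each event. No test of trend is planned, and SAP 5 says that the analyses are not a basis for definitive conclusions. This stands as a limit on the size of the problem: the table is descriptive, and a careful reader could work out the timing. It does not repair the cell. The note to SAP Table 20 counts only subjects with a result at the timepoint, whereas Table 12 counts everyone infused, without comment.

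**All AE rates rise by construction.** A reader might infer this, but the documents do not support it. Vital signs are sampled identically after each dose, and in the 8 g arm cited in Protocol 2.1 decreased heart rate (28.3%) was more frequent than decreased calcium (10.7%). The any-AE row carries an upward bias, not a guaranteed rise.

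**A persisting electrolyte abnormality shows its full rate after Dose 3.** This would count the same AE twice. AEs are recorded with a time of onset and followed to resolution, so one found before Dose 3 is not new at discharge. If 18 subjects are sampled before Dose 3, the printed rate falls from the second window to the third.

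**Laboratory and ECG AEs cannot appear early at all.** This is also too strong. Exit procedures at early termination, an ECG at premature discontinuation, or tests at the investigator's discretion could fall in an earlier window.

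**Conclusion.** The point holds for laboratory and ECG AEs in the per-dose columns of Table 12. As planned, those columns give percentages and exact intervals over subjects of whom 0/30, then 12/30 to 18/30 (five electrolytes only), then 30/30 have a scheduled laboratory test, with all scheduled on-treatment ECGs in the last window. The clearest distortion is the Dose 1 cell: 0/30 with an upper limit of 11.6% and nobody tested. Non-electrolyte laboratory and ECG AEs would appear to arise only after Dose 3 whatever their true onset. For electrolytes the Dose 1 zero is an artifact, but no rise from Dose 2 to Dose 3 follows.

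The coverage counts rest on the schedule alone, for 30 subjects who receive all three doses. The printed rates in steps 5 and 7 rest on the stated assumptions about p, persistence, independence and the 20% clinical rate. The any-time column, which carries the main safety summary, is unaffected. The change should be made, but the overall safety result does not depend on it.

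**What to change.** In SAP 9.3.1 and the Table 12 shell:

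- Flag AEs identified from a laboratory or ECG result, and present them separately from symptom and vital-sign AEs.
- Base the per-dose any-AE comparison on the evenly ascertained AEs only.
- For laboratory and ECG AEs, give the percentage and interval in the any-time column.
- In the per-dose columns for these AEs, print *not assessed* where no test was scheduled: all of them in the Dose 1 window, and non-electrolyte and ECG AEs in the Dose 2 window. List any unscheduled detections there as counts.
- Elsewhere (Dose 2 electrolytes, and everything in the Dose 3 window) use the number of subjects tested in that window as denominator. Printing *not assessed* in these cells would be false.
- Footnote the test timing, and state that no dose-by-dose trend in laboratory or ECG AEs can be drawn. This is still needed with corrected denominators, because the Dose 3 electrolyte cell holds only cases not already recorded.

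No new data are needed, and SAP 15 allows an addendum before final data lock. The cost is one extra AE flag, and per-dose denominators that differ by AE type.

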9.4. Deaths, Serious Adverse Events and other Significant Adverse Events

A listing of SAEs by subject will be presented in Table 14. The listing will include Subject ID, Adverse Event Description, Adverse Event Onset Date/End Date, Days Post Dose, Reason Reported as an SAE, Relationship to Treatment, Alternate Etiology if not Related, action taken with study treatment, whether subject discontinued due to AE, outcome, MedDRA SOC, and MedDRA Preferred Term.

9.5. Pregnancies

For any subjects in the Safety Population who became pregnant during the study, every attempt will be made to follow these subjects to completion of pregnancy to document the outcome, including information regarding any complications with pregnancy and/or delivery. If any pregnancies occur, listings of pregnancies and outcomes will be presented (Listing 20, Listing 21, Listing 22, Listing 23, and Listing 24).

9.6. Clinical Laboratory Evaluations

Chemistry, Hematology, Coagulation, and Urinalysis laboratory parameters will be collected at Screening, Baseline and Day 2 before discharge as described in Section 4.5.1. Sodium, potassium, magnesium, calcium, and phosphorus chemistry parameters will also be collected approximately 2 hours prior to the assigned bronchoscopy timepoint. The grading scale used for clinical laboratory evaluations is presented in Table 3.

Baseline will be defined as the most recent measurement prior to start of infusion of the first ZTI-01 dose. For parameters with multiple pre-dose measurements, screening values prior to the baseline measurement will be listed only.

The following parameters will be presented (in order):

- Chemistry: Sodium, Potassium, Magnesium, Calcium, Phosphorus, Albumin, Random Glucose, BUN, Total Protein, Creatinine, Triglycerides, Total Cholesterol, CPK, ALP, AST, ALT, Total Bilirubin, Direct Bilirubin, and LDH
- Hematology: Hemoglobin, Hematocrit, Platelet Count, WBC Count, Neutrophils, Lymphocytes, Monocytes, Eosinophils, Basophils
- Coagulation: PT and aPTT
- Urinalysis:
- o By dipstick: Leukocyte Esterase, Blood, pH, Specific Gravity, Protein, Glucose.
- By microscopic evaluation: WBC in urine, Red Blood Cells (RBC) in urine, Bacteria, and Casts.

Laboratory results will be summarized by parameter and severity for baseline and all post-dose timepoints (including maximum severity post-baseline) and presented in Table 20, Table 22, Table 24, and Table 26. At baseline, measurements will be summarized according to the grading scale in Table 3. For post-dose measurements, if a value is outside the normal range but did not meet the definition for an AE due to the value being less than or equal to the measurement at baseline, it will be categorized as "Outside Normal Range." All other values will be summarized according to the grading scale in Table 3.

Laboratory parameters that have grading criteria for both decreases (result lower than normal range and baseline measurement) and increases (result higher than normal range and baseline measurement) will be summarized separately by direction of change. For example, sodium will be summarized separately as "Sodium, Decrease" and "Sodium, Increase." For the summary of the Urinalysis laboratory parameters, the denominator for WBC in urine and RBC in urine by microscopic evaluation will be the number of subjects with a urinalysis result (dipstick or microscopic evaluation) for the visit, not only the number of subjects with microscopic evaluation.

Abnormal laboratory results, Grade 1 severity or higher, will be listed in Table 16, Table 17, Table 18, and Table 19.

For continuous laboratory parameters, descriptive statistics including mean, SD, median, min and max values by timepoint and change from baseline all post-dose measures will be presented by laboratory parameter in Table 21, Table 23, Table 25, and Table 27.

Data will be visualized using box plots showing the change from baseline at each post dose timepoint.

- Chemistry Parameters: Beginning at Figure 5 and continuing through Figure 23
- Hematology Parameters: Beginning at Figure 24 and continuing through Figure 32
- Coagulation Parameters: Figure 33, Figure 34
- Urinalysis: Figure 35, Figure 36

Only laboratory parameters reported as continuous values will be included in tables of summary statistics and in box plots for change from baseline. Continuous parameters from the urine microscopic evaluation will not be visualized but will be summarized in the tables of summary statistics.

Listing 9, Listing 10, Listing 11, and Listing 12 will provide a complete listing of individual clinical laboratory results with applicable reference ranges.

Baseline serology screening results (Listing 13), urine toxicology and alcohol screening results (Listing 14) will be listed.

